Most Relevant Preliminary Data: In 2017, out of 401 adolescent patients with suicidality who were in the Cincinnati Children's Hospital's OCIC, only 25 (6%) returned to the ED for psychiatric reasons within 90 days of their first OCIC appointment. Also, the treatment satisfaction ratings by parents were higher for OCIC than inpatient in 2017. For example, significantly more parents (88%) rated that they felt that they participated as much as they should have in OCIC in comparison to inpatient psychiatry (74%). Upon completion of the Dallas OCIC, one of our four sites, teens and parents completed the Client Satisfaction Questionnaire (CSQ-8) CSQ to assess satisfaction. Both patient and parent satisfaction were very high. In response to the question, "In an overall, general sense, how satisfied are you with the service you have received?", 99% of parents and 96% of teens responded that they were mostly satisfied or very satisfied. When asked if they would refer a friend, 89% of parents and 67% of teens responded "definitely yes" while only 1% of parents and 2.3% of teens responded "don't think so". The average score across items on the CSQ for those who were enrolled in the program was 3.78 (SD=.33) for parent (n=290), and 3.54 (SD=.49) for teen (n=302) on a 4 point scale (with 4 indicating the highest level of satisfaction). The findings suggest that OCIC for adolescents with suicidality is both acceptable and feasible as well as efficacious as an alternative to inpatient psychiatry treatment. However, a randomized trial is needed in order to determine the efficacy of OCIC compared to inpatient psychiatry. At our site in Dallas, [name] saw 364 eligible adolescents (aged 12 to 17 years; mean age 14.9 ± 1.4 years) from January 1, 2014 and December 31, 2015 who had a worsening of suicidal ideation or a recent suicide attempt were enrolled in a newly-developed OCIC and attended at least 1 appointment. Suicidality (CHRT-SR) was assessed at baseline and discharge from the program. The majority of patients completed the OCIC program (81.04% over a 4 week period). Patients were improved at the time of discharge on depressive symptoms and suicidal ideation and behavior. Both parents and patients reported significant improvement in depression severity based on the QIDS-A at exit (7.67 ± 4.87 and 8.65 ± 5.58 , respectively) compared to baseline (13.22 ± 4.81 and 13.65 ± 5.98 , respectively), $p < .0001$.

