Scores on the CHRT were also significantly reduced by discharge with propensity scores (26.01 ± 10.43 vs. 16.72 ± 10.03 ; $p < .0001$) as well as active suicidal ideation scores (4.85 ± 3.63 vs. 1.91 ± 2.40 ; $p < .0001$) showing a marked improvement compared to baseline. Preliminary clinical outcomes at discharge from [name]'s OCIC and at six month follow-up were positive. Patients were improved at the time of discharge on self-report of depressive symptoms

and suicidal ideation and behavior. 286 of the 364 adolescents (or 78.57%) responded to the 6 month follow up questions. In total, 8.7% and 27.3% of the 286 respondents reported a suicide attempt and event, respectively, within 6 months of discharge from OCIC. Reattempt rates at 6 months were at 8.7%, with almost half these occurring within one month after discharge. Suicidal events (includes attempts, emergency room visits or hospitalization) at 6 months were at 27.3%. It is possible that the suicidal events were higher than attempts because the adolescents were following their safety plan and reaching out for professional support when suicidal ideation increases. Patients who made an attempt within the 6 month follow up period had a history of more previous attempts, higher self-report of depressive symptoms at discharge, and higher levels of active suicidal ideation (CHRT) at entry and exit.

Those patients who had a suicide event at follow-up were more likely to be female, had more previous attempts, and had higher self-reported and parent reported depression at entry in the program. Those with a suicidal event also had higher self-reported active suicidal ideation at entry into the program.

Due to the fact that telehealth CIS is only currently being widely used for mental health services in this population group, CHRT-SR and other follow up data is not currently known. This research will seek to fill in this gap of knowledge.

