- All screening evaluations must be completed and reviewed to confirm that potential participants meet all eligibility criteria. The investigator will maintain a screening log to record details of all participants screened and to confirm eligibility or record reasons for screening failure, as applicable.
- Time to first recurrence of a suicidal event and number of suicidal events will be measured with the Suicidal Event Form for START (appendix), a short supplemental form (developed by our team), at baseline and every two weeks (see Schedule of Events; appendix)
- Severity of suicidal ideation will be measured with the self-report scale: CHRT-SR (appendix) at baseline and every two weeks (see Schedule of Events; appendix).
- The Suicidal Treatment AlteRnatives for Teens (START)-Clinical Features (CF) form (appendix), a short supplemental form with 13 questions (developed by our team), will be completed at baseline (within 72 hours of admission to inpatient or OCIC) and every two weeks to monitor substance use based on information from patient, parent, and/or EHR.
- The C-SSRS Self-Report form, included in the CF survey, will be completed at baseline and every 2 weeks by the participant to assess for suicidal thoughts and behaviors.
- Satisfaction with Life (SL) will be measured with self-report scales including the PROMIS Short Form v 1.0-General Life Satisfaction-Short Form 5a (to assess the parent's well-being), PROMIS Parent-Proxy Life Satisfaction-Short Form 8a, and PROMIS Pediatric Life Satisfaction-Short Form 4a every 2 weeks.
- Treatment satisfaction (TS) data about, telehealth CIS, OCIC and inpatient psychiatry will be collected only after two weeks and/or subsequent to completion of inpatient psychiatry or OCIC. TS will be measured once with the Client Satisfaction Questionnaire (CSQ-8) 95 after completion of telehealth, OCIC or inpatient treatment which is typically completed by week 3 (but could be completed by week 2 to week 6).
- COVID-19 Impact survey will be completed at week 2 and will gather information regarding the impact of the pandemic on the participant and families social, emotional, and economic functioning.

- The Self-Assessment Manikin (SAM) questionnaire will be completed at baseline and week 12 follow up survey.

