increased risk of serious suicide attempts and suicide.⁶¹⁻⁶³ The cultural context of adolescent suicidal behavior and help-seeking is important and differs among races and ethnic groups.¹⁰⁵ For example, in the Hispanic community, families are much less likely to seek mental health professionals in help seeking and prefer to rely on family first.⁶⁴ Ethnic groups and races differ in rates of adolescent suicidal behaviors.^{105, 106} However, the gap has been decreasing between white adolescent suicides and African American suicides due to an increase in male African American deaths by suicide.⁶⁵⁻⁶⁷ Living situation (living with one biological parent, two biological parents, a stepparent, a relative, or other) is an important HTE for adolescents because living with one parent or the presence of a stepparent was correlated with an increased risk of suicidal thoughts and suicide attempts by adolescents.^{68, 69}

The analysis plan:

To test Aim 1, we will use Cox proportional regression model (CPR) to test whether the telehealth only CIS; outpatient, in-person CIS; and in-patient CIS groups have different incidence rates for recurrent episodes within 3 months. We expect that the sample sizes for the three arms will be *at least* 75, 75, and 70 respectively. To evaluate Aims 2 and 3, we will use the generalized linear model (GLM) to evaluate whether telehealth only CIS; outpatient, in-person CIS; and in-patient CIS groups have different levels of changes in emotional arousal (Aim 2) and treatment satisfaction (Aim 3) at 3 months, after adjusting for several covariates (e.g., age, gender, triage “location”). For CPR, we will have power for our pilot study greater than 0.70 assuming a hazard ratio of 2.8 and greater than 0.8 for our GLM analyses assuming $f^2 = 0.1$ and correcting for multiple comparisons.

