11.1. Appendix 1: Schedule of Events (SoE) / Milestones

Schedule of Events

Measures	Visit (Weeks)											
	Baseline	2	4	6	8	10	12	14	16	18	20	22
Age/Gender/Gender Identity/Insurance Type (Public, Private, No Insurance)/Ethnicity (Hispanic, Non Hispanic)/ Race (African American, Non African American)/ Living Situation (One Parent, Both Parents, Other)												
Demographics Form	x											
Severity of Suicidal Ideation												
CHRT-SR (self-report)-14 item	x	x	x	x	x	x	x	x	x	x	x	x
Suicidal Events												
Suicidal Event Form for START	x	x	x	x	x	x	x	x	x	x	x	x
Substance Use												
Clinical Features (CF)	x	x	x	x	x	x	x	x	x	x	x	x
Treatment Satisfaction												
Client Satisfaction Questionnaire (CSQ-8)		x										
Satisfaction with Life												
PROMIS Short Form-Life Satisfaction (SL)	x	x	x	x	x	x	x	x	x	x	x	x
PROMIS Parent-Proxy SL-Short Form 8a	x	x	x	x	x	x	x	x	x	x	x	x
PROMIS Pediatric SL-Short Form 4a	x	x	x	x	x	x	x	x	x	x	x	x
Other												
COVID-19 Survey		x										
Self Assessment Manikin (SAM)	x						x

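### CSQ-8 timing is stated in four incompatible ways and is undefined for patients who stop treatment early, so the Aim 3 contrast of telehealth or OCIC with inpatient care could be biased.

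*Combined protocol and SAP*

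**What the plan says.** The combined protocol and SAP times the treatment satisfaction measure in four places.

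- **Section 8, Study Assessments and Procedures, first sentence on satisfaction:** data "will be collected only after two weeks and/or subsequent to completion of inpatient psychiatry or OCIC". The completion clause here does not list telehealth.
- **Section 8, next sentence:** "TS will be measured once with the Client Satisfaction Questionnaire (CSQ-8) 95 after completion of telehealth, OCIC or inpatient treatment". Treatment is said to be "typically completed by week 3 (but could be completed by week 2 to week 6".
- **Appendix 1, Schedule of Events:** the row "Client Satisfaction Questionnaire (CSQ-8") has one mark, at week 2, with no condition on completion.
- **Section 9.2.3, analysis plan (also section 4.2):** a GLM compares the three groups on "changes in emotional arousal (Aim 2) and treatment satisfaction (Aim 3) at 3 months". The week-12 column of the Schedule of Events has no CSQ-8.

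Other sections bear on this:

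- Section 6.2 keeps participants who miss appointments, refuse treatment or leave against medical advice in follow-up. It does not mention the CSQ-8.
- Section 6 lists inpatient stays of 6 to 8 days, and 4-6 weeks for OCIC and telehealth in Dallas. Three sites describe an average of 1-3 sessions.
- Section 2.2 reports for the Dallas OCIC: "The majority of patients completed the OCIC program (81.04% over a 4 week period"). For telehealth it says that "CHRT-SR and other follow up data is not currently known".
- Section 3 (SA3) hypothesises lower satisfaction with telehealth than with inpatient care or in-person OCIC.
- Section 9.2 leaves missing-data procedures to a later SAP.

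**The concern.** Aim 3 rests on one CSQ-8 per participant, so the rule for when it is sent also decides who is in the analysis. The two main readings fail in different ways.

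**Completion trigger.** A participant who leaves a multi-visit outpatient programme does not complete it and may never be sent the form. A 6-8 day stay offers fewer chances to stop, since only a discharge against medical advice counts as non-compliance there. If early stoppers are less satisfied, low scores are lost mainly from the outpatient arms. That would flatter telehealth and OCIC against inpatient care and could hide the deficit that SA3 expects. Adjustment for age, gender and triage location does not correct selection that depends on satisfaction itself.

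**Week-2 mark.** Early stoppers can be asked, but the arms are then scored at different stages of care. Telehealth is expected to be scheduled within 7 business days of assessment, so at week 2 a patient in a 4-6 week programme has had only part of it. An inpatient has normally been discharged.

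The later SAP can choose how to handle missing scores. It cannot recover a form that was never sent.

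**Working it through.** **1. The plan's own figure.** Section 9.1 gives power 0.84 for a continuous outcome with d = 0.5 and groups of 75 and 70. Alpha is taken as two-sided 0.05, which section 9.1 states for the survival comparison. Two-sample t test: noncentrality = 0.5 x sqrt(75 x 70 / 145) = 0.5 x 6.017 = 3.01, df = 143, power 0.848. The figure reproduces.

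**2. Inputs for the completion trigger.**
- Dallas in-person OCIC non-completion (section 2.2): 1 - 0.8104 = 0.1896.
- Telehealth completion, completion at other OCIC sites, and the rate of discharge against medical advice: not given.
- Lower value for outpatient loss, by assumption: the Dallas rate at Dallas, none elsewhere, equal site shares (section 1 plans 61 of 244 per site). 0.1896 x 61/244 = 0.047, about 5%.
- Gap g between completers and early stoppers, in SD: not given. Assumed range 0 to 1.

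**3. Formula.** With share q unscored and gap g, the mean of all treated patients is the completer mean minus q x g. Scoring completers only therefore overstates an arm by q x g, and

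bias (outpatient minus inpatient) = (q_out - q_in) x g.

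The scored sample is 75 x (1 - q_out) against 70 x (1 - q_in). Type I error is the two-sided rejection rate when the true difference is zero and the observed difference equals the bias. Power is for telehealth truly lower by 0.5 SD, so the observed deficit is 0.5 minus the bias.

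**4. Worked case.** q_out = 0.1896, q_in = 0: scored 60.78 vs 70, and sqrt(60.78 x 70 / 130.78) = 5.704. At g = 1 the bias is 0.1896 SD and the noncentrality at no true difference is 0.1896 x 5.704 = 1.08, which gives a type I error of 0.189.

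| q_out | q_in | g (SD) | Bias (SD) | Type I error | Power at d = -0.5 |
|---|---|---|---|---|---|
| 0.19 | 0 | 0 | 0 | 0.050 | 0.81 |
| 0.19 | 0 | 0.5 | 0.09 | 0.084 | 0.63 |
| 0.19 | 0 | 1.0 | 0.19 | 0.189 | 0.42 |
| 0.19 | 0.10 | 0.5 | 0.04 | 0.057 | 0.71 |
| 0.19 | 0.10 | 1.0 | 0.09 | 0.078 | 0.62 |
| 0.10 | 0 | 0.5 | 0.05 | 0.060 | 0.75 |
| 0.10 | 0 | 1.0 | 0.10 | 0.090 | 0.64 |
| 0.05 | 0 | 0.5 | 0.02 | 0.052 | 0.80 |
| 0.05 | 0 | 1.0 | 0.05 | 0.059 | 0.76 |

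(The 0.19 rows use 0.1896 and the 0.05 rows use 0.0474.)

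On the teen item mean (SD 0.49, section 2.2), the largest bias is 0.1896 x 0.49 = 0.09 points on the 4-point scale.

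**5. What drives the result.** Losing 19% of outpatient scores with no gap moves power only from 0.85 to 0.81. The rest comes from the assumed gap. With equal loss in two arms and equal gaps the bias is zero, so it may cancel for telehealth versus OCIC. If inpatient loss exceeded outpatient loss, the sign would reverse.

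**6. Week-2 mark.** The documents give no data on how CSQ-8 scores change during care, so neither the direction nor the size can be computed.

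**The case against.** A reader might infer that the plan settles on completers only, so that about 19% of outpatients have no Aim 3 outcome and the comparison is biased towards telehealth and OCIC. The documents do not support that.

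- The sentence before the completion sentence lets two weeks serve as an alternative, and the Schedule of Events sets no completion condition. Section 8 calls adherence to that schedule essential. With non-compliant patients kept in follow-up, early stoppers could well be asked.
- The 19% belongs to one site's in-person programme with 9 group hours a week over 4-6 weeks. Where care averages 1-3 sessions, one or two visits can be a full course. No telehealth rate is given, and SA3 is about telehealth.
- No passage reports satisfaction by completion status. Stopping early could also reflect improvement or transfer to inpatient care. Zero inpatient loss is likewise an assumption.
- The group sizes of 75, 75 and 70 already allow for 10% dropout, which may overlap with treatment non-completion.

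All of this stands, and it limits the claim to a possible bias of uncertain size. It does not remove the conflict. The and/or wording sets no rule, the following sentence narrows it to one measurement after completion, and the week-2 mark brings its own imbalance in stage of care. Nothing in the plan says when, or whether, an early stopper receives the form.

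**Conclusion.** The concern holds as a conflict over timing with a possible selective loss of scores. It does not hold as a demonstrated bias. The four timings cannot all be followed, and the two that sites are most likely to follow each leave the outpatient-versus-inpatient contrast open to bias. Under the completion trigger the bias probably favours telehealth and OCIC, provided that early stoppers are less satisfied and inpatient loss is lower.

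With outpatient loss of 5% to 19%, a gap of 0 to 1 SD and no inpatient loss, the bias is 0 to 0.19 SD and the type I error 0.05 to 0.19. At 19% loss, power to show a 0.5 SD telehealth deficit is 0.81 with no gap and 0.42 with a 1 SD gap. The figures at 19% loss with gaps of 0.5 to 1 SD are upper-end scenarios, because they apply the Dallas rate everywhere. At 10% inpatient loss and the same gaps, the bias falls to 0.04 to 0.09 SD. The change should be made because it is cheap, and scores not requested during follow-up cannot be recovered at analysis.

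**What to change.** - **Section 8:** replace both timing sentences with one rule for all arms. Request the CSQ-8 from every participant who attended at least one telehealth or OCIC session or was admitted, regardless of completion, at the end of care or when care stops early, and no later than the week-6 survey.
- **Appendix 1:** change the CSQ-8 row to match.
- **Sections 4.2 and 9.2.3:** replace the 3-month wording for Aim 3 with the same time point.
- **Analysis:** run the Aim 3 GLM on all ever-treated participants, report CSQ-8 missingness by arm, and give a completers-only result as a sensitivity analysis.

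The cost is a wording change in these sections and a changed REDCap trigger for a form already in use. Two drawbacks remain. Some scores will come from patients with little exposure to the service, and a patient still in a 4-6 week programme at the week-6 limit will be scored near the end of care instead of after it.

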8.1. Efficacy Assessments

- Time to first recurrence of a suicidal event and number of suicidal events will be measured with the Suicidal Event Form for START (appendix), a short supplemental form (developed by our team), at baseline and every two weeks (see Schedule of Events; appendix)
- Severity of suicidal ideation will be measured with the self-report scale: CHRT-SR and C-SSRS (appendix) at baseline and every two weeks (see Schedule of Events; appendix).
- The Suicidal Treatment AlteRnatives for Teens (START)-Clinical Features (CF) form (appendix), a short supplemental form with 13 questions (developed by our team), will be completed at baseline (within 72 hours of admission to inpatient, telehealth CIS, or OCIC) and every two weeks to monitor substance use based on information from patient, parent, and/or EHR.
- Satisfaction with Life (SL) will be measured with self-report scales including the PROMIS Short Form v 1.0-General Life Satisfaction-Short Form 5a (to assess the parent's well-being), PROMIS Parent-Proxy Life Satisfaction-Short Form 8a, and PROMIS Pediatric Life Satisfaction-Short Form 4a every 2 weeks.

8.2. Adverse Events

The primary outcomes in this study, suicidal ideation or a recent suicide attempt, are AEs that will be reported to the DSMB. In addition, youth at risk for suicide often engage in multiple health risk behaviors (e.g., alcohol/drug use, interpersonal violence) and consequently, are at increased risk for accidental injury and death, all of which constitute AEs or SAEs. We expect AEs and SAEs in this population, but not related to study procedures.

Prior to recruitment, the DSMB will meet in the first month to review the protocol, outcomes, AE and SAE definitions, and treatment components to ensure there are no concerns.

AE will be reported by the participant (or, when appropriate, by a caregiver, surrogate, or the participant's legally authorized representative).

If the AEs and SAEs are related to study procedures, then we will review with the DSMB. We will also review the proportion of observed suicidal-related AEs in our study compared to the rate of suicidal ideation and suicide attempts we would expect in this population, based on the extant literature.

8.2.1. Time Period and Frequency for Collecting AE and SAE Information

All AE and SAE will be collected from the start of treatment until 180 day follow-up or when the participant completes milestones.

For serious adverse events that result in injury, disability, death or significant functional impairment, each site is required to notify the DSMB and the IRB within 24-48 hours of the knowledge of the occurrence one of these SAE's, how the site personnel became aware of it, and

the response. The DSMB will make a determination as to whether the risks and benefits of the study are altered by the event.

